#### 4.1.1 Experience with the use of convalescent plasma against coronavirus diseases

In the 21st century, there were two other epidemics with coronaviruses that were associated with high mortality, SARS1 in 2003 and MERS in 2012. In both outbreaks, the high mortality and absence of effective therapies led to the use of convalescent plasma. The largest study involved the treatment of 80 patients in Hong Kong with SARS [8]. Consistent with historical data that earlier administration of antibody is more likely to be effective, 30 patients treated a mean of 11.7 (+/- 2.3) days after symptom onset had improved prognosis defined by discharge from hospital before day 22, whereas 47 patients who received plasma a mean of 16 days after symptom onset died before day 22 or had a late discharge. The mortality rates in the two groups were 6.3% and 21.9%, respectively (P=0.08), and those who were nasal swab PCR positive and seronegative for coronavirus at the time of therapy had improved prognosis. There is also some anecdotal information on the use of convalescent plasma in seriously ill individuals. Three patients with SARS1 in Taiwan were treated with 500 ml of convalescent plasma, resulting in a reduction in plasma virus titer and each survived [9]. Three patients with MERS in South Korea were treated with convalescent plasma, but only two of the recipients developed neutralizing antibody one week after infusion [10]. The latter study highlights a challenge in using convalescent plasma; some who recover may not have high titers of neutralizing antibody [11]. In addition, only 2 of 4 donor plasma infusions showed neutralizing antibody activity. This is consistent with an analysis of 99 samples of convalescent sera from patients with MERS which showed that 87 had neutralizing antibody with a geometric mean titer of 1:64. This suggests that antibody declines with time and/or only a few patients make high titer responses. Our study addresses this issue by screening plasma for antibody to SARS-CoV-2 and will only use plasma with SARS-CoV-2 antibodies detected. However, it is possible non-neutralizing antibodies may also contribute to protection as described for other viral diseases [12, 13]. In addition, to ensure that the control arm plasma does not have SARS-CoV-2 antibodies present, control fresh frozen plasma will be used from prior to December, 2019 or testing for SARS-CoV-2 antibodies in the control plasma will be performed immediately prior to administration.

A recently performed pilot study in Wuhan, China collected convalescent liquid plasma from COVID-19 positive patients 3 weeks following the onset of illness and 4 days post-discharge and treated patients diagnosed with 'severe COVID-19' as defined by WHO Interim Guidance and the Guideline of Diagnosis and Treatment of COVID-19 National Health Commission of China [14]. Ten patients were treated with one dose of convalescent plasma (200ml, >1:640 titer by neutralization assay) at a median of 16.5 days (11-19.3 days) post-onset of symptoms. A COVID-19 positive control cohort was retrospectively identified and matched by demographics, comorbidities, and severity of illness. There were no serious adverse reactions or safety events recorded with convalescent plasma, including no reported transfusion related reactions, transfusion-related acute lung injury, or antibody-mediated enhancement of infection. In the treatment group, there were 0 deaths, 3 discharges and 7 patients improved, whereas there were 3 deaths and 7 patients who improved in the control group (p < 0.001). In addition, 2 of 3 patients in the treatment on mechanical ventilation were weaned to high flow nasal cannula, which was discontinued in one patient. There was a reduction in blood RNA viral load in 7 of 10 patients on day 6 post-convalescent plasma therapy as well as improvement in laboratory markers. There were also varying degrees of improvement in pulmonary lesions on chest CT after convalescent plasma therapy. In another case series from China, five severely ill patients with COVID-19, all on mechanical ventilation received convalescent plasma within 22 days of admission [15]. Temperatures normalized in 4 of 5 patients within 3 days, SOFA scores decreased, and there was improvement in oxygenation and ARDS resolution. All survived, with 3 discharged home and 2 in stable condition. These reports suggest convalescent plasma may hold promise for ameliorating the severity of Covid-19 and deserves immediate investigation for this indication.

#### 4.1.2 Known potential risks

A theoretical risk of administration of convalescent plasma is the phenomenon of antibody-mediated enhancement of infection (ADE). ADE can occur in viral diseases, such as dengue and involves an enhancement of disease in the presence of certain antibodies. For coronaviruses, several mechanisms of ADE have been described, including the theoretical concern that antibodies to one type of coronavirus could enhance infection to another strain [16]. It may be possible to predict the risk of ADE in SARS-CoV-2 experimentally, as proposed for MERS [16]. Since the proposed use of convalescent plasma in the COVID-19 epidemic would rely on preparations with high titers of antibody against the same virus, SARS2-CoV-2, ADE may be unlikely. Available evidence from the use of convalescent plasma in patients with SARS1 and MERS [17] demonstrated it is safe and there were no adverse effects in a pilot study of patients with COVID-19 [14]. Nevertheless, caution and vigilance will be exercised to use clinical and laboratory measures to detect evidence of enhanced infection.

Another theoretical risk is that CCP to those exposed to SARS-CoV-2 may prevent disease but modify the immune response such that those who are treated may mount attenuated immune responses. This may leave them vulnerable to subsequent re-infection. Passive antibody administration before vaccination with respiratory syncytial virus attenuated humoral but not cellular immunity [18]. This will be investigated as part of this clinical trial by comparing immune responses in those who receive standard plasma and convalescent plasma. If responses differ, those with attenuated levels could be vaccinated against COVID-19 when a vaccine becomes available. Nonetheless, these concerns are modest compared to the possible benefit of reducing the risk of respiratory failure and avoiding mechanical ventilation.

Finally, there are risks associated with any transfusion of plasma including transmission of transfusion transmitted viruses (e.g. HIV, HBV, HCV, etc.), allergic transfusion reactions, anaphylaxis to transfusion, febrile transfusion reaction, transfusion related acute lung injury (TRALI), transfusion associated cardiac overload (TACO), and hemolysis should ABO incompatible plasma be mistakenly administered. To minimize the risks of disease transmission, all plasma donors will be required to meet full allogeneic blood donation requirements as determined by FDA and the collection center. Donors are screened for behavioral risk factors for bloodborne infections using the standard blood donor history questionnaire (DHQ) and extensive testing for blood borne pathogens using FDA-licensed tests for blood product testing. In addition, donors will fulfill all FDA convalescent donor requirements which require a history of COVID19 illness (documented by positive COVID-19 test at time of illness OR positive COVID-19 serology) and complete resolution of symptoms at least 28 days prior to donation, or complete resolution of symptoms at least 14 days prior to donation with negative COVID-19 nasopharyngeal swab or molecular diagnostic test from blood[19].

A recent observational series described the safety of CCP administered to over 5000 hospitalized patients with COVID-19 infection. The incidence of adverse events in the day after plasma infusion was < 1% with only 2 of 36 events attributed to CCP by the treating clinician, suggesting a favorable initial safety signal and no clear evidence of ADE. [20]

#### 4.1.3 Known potential benefits

The most important potential benefit is that convalescent plasma may reduce progression to respiratory failure in patients with COVID-19 and early respiratory symptoms, such as shortness of breath, cough, chest pain, and pulmonary infiltrates. The benefit of plasma is expected to be an improvement in symptoms, oxygenation, the need for mechanical ventilation and possibly reduced mortality. Based on historical experience with antibody administration, antibody administration is expected to be effective relatively early in disease [2]. Convalescent plasma was safe, reduced symptoms, and improved oxygenation in a non-randomized open label study of patients with more advanced disease in Wuhan, China [14].

[figure not shown]
Given historical data showing convalescent plasma was safe and possibly effective in patients with SARS1 [8, 17], and emerging data from China suggest it is safe and possibly effective in patients with severe COVID-19, the benefits of its use in those at high risk for severe disease outweigh the risks. However, for all patients in whom convalescent plasma administration is considered, a risk-benefit assessment will be conducted to assess individual variables. This protocol proposes a randomized controlled pragmatically blinded trial to assess the efficacy of convalescent plasma in preventing severe hypoxemia in patients with COVID-19. A JAMA editorial by experts note the importance of randomized clinical trials to demonstrate efficacy of this approach and change the course of the epidemic [21].

# 4.1.4 **Target population**

This study will enroll hypoxic hospitalized COVID-19 patients, a group that is at elevated risk for poor outcomes and progressive respiratory failure. To date, approximately 30-50% of hospitalized San Francisco COVID-19 patients have required intensive care level treatment, the majority due to respiratory failure[1]. This high progression to ICU level care due to respiratory failure has been seen across the US. This study targets patients who are still early in the course of disease, when CCP may be most effective, the "green zone" described in Figure 2. Once severe respiratory decompensation and ARDS occur and patients have progressed to the "red zone", CCP may be less effective, as was the case with use of CCP in SARS-1 -[8]. The study has been amended to include those on high flow nasal oxygenation, as well as those on nasal cannula. In the ACTT-1 study, 25% of participants on HFNC (ordinal group 6) progressed to mechanical ventilation or death [22] These individuals are at elevated risk of progression to intubation and it is important to understand if CCP can reduce deterioration of respiratory status.

This study will permit enrollment of pregnant women, breastfeeding women and women of childbearing potential. CCP should not pose a pregnancy specific risk, other than the known risks associated with blood product infusions in general. However, for pregnant or breastfeeding women, additional counseling will be provide as to the lack of data for CCP use in COVID-19 infection during pregnancy and lactation and that an adverse event that impacts the participant could also affect an unborn child by affecting maternal health. Pregnant women who chose to enroll will have the pregnancy outcome recorded.

# Figure 1: San Francisco COVID Data Tracker: Total COVID acute care beds and subset of ICU beds [1].

**Figure 2.** Natural history of COVID-19 infection with a biphasic initial mild disease (green zone) and subsequent severe respiratory failure (red zone)[23]

lea lea ur nai	features according to current tions an (SD) 55,5 (13-1). Male (68%) re to Huanan seafood market n, China (49%) medical underlying illness (51%) on to Intensive Care Unit (23%)	ALL OF				(-)			
			FIRST	WEEK			SECON	D WEEK	
	SETTING	WARD Illness day 4	WARD Illness day 5	WARD Illness day 6	WARD Illness day 7	WARD/ICU Illness day 8	ICU Illness day 9	ICU Illness day 10	ICU Illness day 11
REPEATED SAMPLING OF THE NASOPHARYNX AND TRACHEAL ASPIRATES (IF INTUBATED) BY INTP-CR FOR THE COVID-19 OXYGEN THERAPY AND		t viral shedding	Decrease of the viral shedding sometimes associated with transient respiratory deterioration		Respiratory failure, increase of the viral shedding and viremia or Decrease of the viral shedding, and superinfections			Duration of viral excretion unknown	
	OXYGEN THERAPY AND MECHANICAL VENTILATION	NO		Consider oxygen support	FNC	FNC followed by MV	MV		MV
	ORGAN FAILURE	Typical signs according Fever, cough, and short bilateral pneumonia (75% lymphopenia (35%), thrc prothrombin time decrea elevated liver enzyme le	%), imbocytopenia (12%), sed (30%),	Deterioration of r with most often spo			ARDS If shock beware of superinfections Possible renal failure Neurological failure unlikely Hernostasis disorders		YES
	CO-INFECTION/SUPERINFECTION	NOT L		LIKELY		Consider a possible HAP/VAP and other nosocomial infections (see text for diagnostic procedures)			Profound immune paralysis and late onset infections
	ANTIBIOTICS		N	NO		Consider antibiotic therapy			YES
CO-INFECTION/SUPERINFECTION ANTIBIOTICS ANTIVIRAL AGENTS		NO			Consider antiviral agents if deterioration a			-	

# 4.1.7 Viral load testing

Serial nasopharyngeal testing will be conducted to evaluate SARS-CoV-2 viral decline in each arm. Metagenomic next generation sequencing (mNGS) will be conducted on PCR specimens. mNGS enables simultaneous profiling of host gene expression and viral load, and assessment of the SARS-CoV-2 viral genome. This approach will enable broad detection of host transcriptional biomarkers that may correlate with treatment outcomes, and may reveal biological mechanisms underpinning CCP antiviral activity. mNGS will additionally provide an opportunity to assess whether SARS-CoV-2 viral load and genotype correlate with clinical outcomes and treatment response.

# 4.1.8 Adaptive trial design

This trial is designed as a randomized controlled trial of CCP versus a control arm of plasma without SARS-CoV-2 antibodies. At this time, the antiviral remdesivir (RDV) will be permitted, as has demonstrated a 31% faster time to recovery with RDV vs. placebo in preliminary data from a randomized controlled trial of hospitalization in COVID-19 patients [24]. The preliminary mortality rate of 8% in the RDV arm indicates that hospital-based RDV administration alone was not sufficient to mitigate morbidity/mortality associated with severe COVID-19 disease. Should the data from the ACTT studies or other RDV study indicate a substantial reduction in progression to severe hypoxemia in the target population of hospitalized hypoxic COVID-19 patients, the sample size will be recalculated with a potential increase if necessary.

Preliminary findings from the open label, randomized RECOVERY study have demonstrated a mortality reduction with dexamethasone use compared to standard of care, 29% vs 41.1% respectively, rate ratio of 0.64 [95% CI 0.0.51 to 0.81] [26]. A smaller mortality reduction was reported in hypoxic patients of 23.3% vs 26.2%, rate ratio of 0.82 [95% CI 0.07 to 0.94] with no data are available on those on lower vs higher level of oxygen support. Given the modest benefit in non-ICU patients, this protocol will exclude use of dexamethasone for COVID treatment at the time of enrollment. Participants with progressive disease who reach the study hypoxemia endpoint can receive dexamethasone, at the discretion of the treating provider. Of note, our institutional practice does not treat all hospitalized patients with dexamethasone as standard of care.

Other investigational or off label interventions will not be permitted during the first 15 days unless the study subject meets the primary endpoint of progression to mechanical intubation. Should evidence become available during the study to support the use of anti-COVID-19 therapeutics, including antivirals and/or immune modulators that improve clinical outcomes and/or significantly reduce viral load, the study will incorporate these therapies into the study design, with a recalculation of the sample size. Given the

substantial risk for decompensation, hospitalized hypoxic COVID-19 may benefit from CCP in addition to other effective treatment, which may further reduce the risk of respiratory decompensation.

# 4.1.9 Collaboration with longitudinal cohorts and data pooling efforts

Participants will be encouraged to enroll in a longitudinal observational cohort conducted by collaborating investigators with aligned specimens collections to facilitate translational evaluations and long term follow-up of immunologic and clinical outcomes.

Data from this protocol will be pooled with other similar studies of CCP in hospitalized hypoxic individuals enrolled in randomized controlled trials of CCP vs. control. Data shared will be de-identified and contain no protected health information (PHI).

#### 4.1.10 Future direction

This proof-of-concept clinical trial will lay the foundation for a future study that may incorporate hyperimmune IgG and/or monoclonal antibodies, when available, along with anti-COVID agents (either anti-viral and/or anti-inflammatory strategies) as emerging data are available to support use as standard of care. This initial study will provide much needed infrastructure and preliminary data to support larger, multicenter trials using either convalescent plasma or hyperimmune IgG across the greater SF Bay Area.

# 5 INVESTIGATIONAL PLAN:

# 5.1 Study objectives

OBJECTIVES	ENDPOINTS (OUTCOME MEASURES)
Primary Objective	
Evaluate the efficacy of convalescent fresh frozen plasma from blood donors who have recovered from Covid-19 containing antibodies to SARS-CoV-2 versus control (standard fresh frozen plasma) to prevent mechanical intubation within 14 days of CPP administration in hospitalized patients with COVID-19 who are within 3 days of hospital admission or 14 days of symptom onset.	Progression to mechanical intubation or death within the first 14 days of enrollment. A secondary endpoint will evaluate progression to endpoint within the first 28 days of enrollment.
Key Secondary Objectives	
To evaluate the clinical efficacy of CCP relative to the control arm in adults hospitalized with COVID-19 according to clinical status (8-point ordinal scale) at Day 29	
 
Death;
 
Hospitalized, on invasive mechanical ventilation or ECMO;
 
Hospitalized, on non-invasive ventilation or high flow oxygen devices;
 
Hospitalized, requiring supplemental oxygen;
 
Hospitalized, not requiring supplemental oxygen - requiring ongoing medical care (COVID-19 related or otherwise);
 
Hospitalized, not requiring supplemental oxygen - no longer requires ongoing medical care;
 
Not hospitalized, limitation on activities and/or requiring home oxygen;
 
Not hospitalized, no limitations on activities.
 

OBJECTIVES	ENDPOINTS (OUTCOME MEASURES)
Additional Secondary Objectives	

 
To evaluate the clinical efficacy of different investigational therapeutics as compared to the control arm as assessed by:
 
Clinical Severity Ordinal scale:
 
Time to an improvement of one category and two categories from Day 0 (baseline) using an ordinal scale.
 
Subject clinical status using ordinal scale at Days 2,5,8,15, 29
 
Mean change in the ordinal scale from Day 1 to Days 2,5,8,15, 29
 
	
 
Clinical outcome assessed using ordinal scale daily while hospitalized and on Days 15, 29 and 120
 
Time to clinical recovery (defined as ordinal score 1-3)
 

 
National Early Warning Score (NEWS):
 
Time to discharge or to a NEWS of ≤ 2 and maintained for 24 hours, whichever occurs first.
 
Change from Day 1 to Days 2,5,8,15, 29
 
	
 
NEWS assessed daily while hospitalized
 


 
Oxygenation:
 
Oxygenation use up to Day 90.
 
Incidence and duration of new oxygen use during the study.
 
Oxygen requirement on day 1,2,5,8,15, 29
 
	
 
Days of supplemental oxygen (if applicable) up to Day 29
 
PaO2/FiO2 ratio or SpO2/FiO2
 
O2 requirement at day 120
 

 
Non-invasive ventilation/high flow oxygen:
 
Non-invasive ventilation/high flow oxygen use up to Day 29.
 
Incidence and duration of new non-invasive ventilation or high flow oxygen use during the study.
 
	
 
Days of non-invasive ventilation/high flow oxygen (if applicable) up to Day 29
 

 
Invasive Mechanical Ventilation / extracorporeal membrane oxygenation (ECMO):         
 
Ventilator / ECMO use up to Day 29.
 
Incidence and duration of new mechanical ventilation or ECMO use during the study.
 
 
 
	
 
Days of invasive mechanical ventilation/ECMO (if applicable) up to Day 29.
 

 
Hospitalization
 
Duration of hospitalization (days).
 
	
 
Days of hospitalization as of Day 29 and day 120
 

Mortality 
 
15-day mortality
 
29-day mortality
 
120-day mortality
 
	
 
Date and cause of death (if applicable)
 

To evaluate the safety of CCP as compared to the control arm as assessed by:	• SAEs

 
Cumulative incidence of SAEs through Day 29.
 
Cumulative incidence of Grade 3 and 4 clinical and/or laboratory AEs through Day 29.
 
Transfusion associated adverse events
 
	
 
Grade 3 and 4 AEs
 
Grade 2 or higher AE's attributed to CCP
 

 
Exploratory Objectives         
 
To evaluate the virologic efficacy of CCP as compared to the control arm as assessed by:
 
 
 
Percent of subjects with SARS-CoV-2 detectable in NP/MTN sample at Days 1,5,8,15
 
Quantitative SARS-CoV-2 virus in NP/MTN sample at Days 1,2, 5,8,15
 
	
 
Qualitative and quantitative polymerase chain reaction (PCR) for SARS-CoV-2 in NP/MTN swab on Day 1,2,5,8,15 (while hospitalized)
 

# 5.2 Study Definitions

- *Enrolled*: From time consented to participate until designated as (i) ineligible based on the inclusion/exclusion criteria or withdraws, (ii) been discontinued from the study or (iii) completed the study.
- Randomized: when a randomization number is assigned.
- Screen Failures: signed informed consent, but then determined to be ineligible or withdraws before being randomized.
- Discontinued: randomized, but then withdrawn by investigator or subject withdraws consent
- Completed: Subjects are considered completed when they are followed through to day 29, had an adverse event or death occurred prior to day 29. Patients will be asked to have day29 and day 120 study visits as well.

# 5.3 Study Population

# 5.3.1 Inclusion Criteria for Enrollment:

- 1. Patients ≥18 years of age
- 2. Hospitalized with COVID-19
- 3. Enrolled within 72 hours of hospitalization OR within day 14 from first signs of illness
- 4. Pulmonary infiltrates on chest imaging
- 5. Oxygenation of <95% on room air
- 6. Laboratory confirmed COVID-19

#### 5.3.2 Exclusion Criteria

1. Contraindication to transfusion due to inability to tolerate additional fluid, such as due to decompensated congestive heart failure

2. Baseline requirement for oxygen supplementation prior to COVID-19 infection or use of positive pressure therapy for sleep disordered breathing

- 3. Currently experiencing severe hypoxemic failure, as defined in study endpoints
- 4. Prior receipt of plasma products, IVIG, or hyperimmune globulin within past 3 months
- 5. Currently enrolled another interventional clinical trial of COVID-19 treatment.

Note: If taking medications with potential anti-COVID activity that do not have data to support efficacy, such as IL-6 antagonists, these medications must be stopped prior to enrollment. Receipt of current standard of care COVID-19 treatment, including remdesivir is permitted and should be recorded as a concomitant medication.

Note: Pregnancy is not exclusionary but will merit additional discussion of risks & benefits in the context of ongoing pregnancy

# 5.3.3 Subject Withdrawal

- 1. Subjects can terminate study participation and/or withdraw consent at any time without prejudice.
- 2. Randomized subjects who withdraw from the study will be replaced

3. The investigator may withdraw subjects if they are non-compliant with study procedures or if the investigator determines that continued participation in the study would be harmful to the subject or the integrity of the study data

Discontinuation of the study: The study sponsor, FDA and IRB all have the right to terminate this study at any time

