# 6.2 Statistical Analysis

# 6.2.1 **Primary endpoint**

Our primary hypothesis is that by providing anti-SARS-CoV-2 plasma, the rate of progression to mechanical ventilation or death will be decreased as compared to the rate in in the group receiving control plasma. We will apply a Fisher exact test to compare the combined endpoint of mechanical ventilation/death respiratory failure rates between the two groups occurring by day 15. 29. All analyses

will be conducted with a modified intention-to-treat approach, which excludes randomized subjects who do not initiate an infusion of the study plasma. As secondary analysis, we will also analyze the reduced oxygenation rate, requirement for supplemental oxygen rate, length of hospitalization, time to recovery (ordinal score 1-3) and mechanical ventilation rate, respectively, as well as occurrence of the primary endpoint by day 29 Statistical inference will be based on a two-sided Type 1 error rate of 0.05 and 95% confidence intervals.

Participants who are intubated for reasons other than hypercarbia/hypoxia, such as for a procedure or airway obstruction, will have ventilation settings evaluated to determine if need for ventilation due to hypoxia is meet. This will be determined by >12 hours of requirement for a mandatory mode of ventilation (volume control or pressure control) or Fi02 of > 40%. External adjudication of intubation for non-hypoxic/hypercarbic indication will be conducted.

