# 7.2 Definitions

1. **Adverse Event (AE):** Any untoward medical occurrence in a clinical investigation subject who has received a study intervention and that does not necessarily have to have a causal relationship with the study product. An AE can, therefore, be any unfavorable and unintended sign (including an abnormal laboratory finding, for example), symptom, or disease temporally associated with the use of the study product, whether or not considered related to the study product.

2. Serious Adverse Event (SAE): Any adverse event that results in any of the following outcomes:

- 1. Death
- 2. Life-threatening (immediate risk of death)
- 3. Prolongation of existing hospitalization
- 4. Persistent or significant disability or incapacity

5. Important medical events that may not result in death, be life threatening, or require intervention or escalation of care may be considered a serious adverse event when, based upon appropriate medical judgment, they may jeopardize the subject and may require medical or surgical intervention to prevent one of the outcomes listed in this definition. Examples of such medical events include allergic bronchospasm requiring intensive treatment in an emergency room or at home, blood dyscrasias or convulsions that do not result in inpatient hospitalization.

- 3. **Unexpected Adverse Event (UAE):** An adverse reaction, the nature or severity of which is not consistent with the investigator's brochure.
- 4. Serious and Unexpected Suspected Adverse Reaction (SUSAR): An adverse reaction, the nature of which is not consistent with the investigator's brochure with severity as defined by SAE above.
- 5. Unanticipated Problem (UP): Unanticipated Problem that is not an Adverse Event (e.g. breaches of confidentiality, accidental destruction of study records, or unaccounted-for study drug).
- 6. **Protocol Deviation:** Deviation from the IRB-approved study procedures. Designated serious and nonserious
- 7. Serious Protocol Deviation: Protocol deviation that is also an SAE and/or compromises the safety, welfare or rights of subjects or others

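### Replacement of withdrawn patients is not limited to those not yet infused, and the plan does not say how infused patients who leave before Day 15, or their replacements, are followed and counted

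*Combined protocol and SAP*

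**What the plan says.** **Withdrawal and replacement (5.3.3).** Patients may leave at any time. The next item reads "Randomized subjects who withdraw from the study will be replaced". It sets no time limit and does not separate patients who leave before the infusion from those who leave after it. A further item reads "The investigator may withdraw subjects if they are non-compliant with study procedures", and also allows withdrawal on grounds of harm or data integrity. That item does not mention replacement.

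**Status labels (5.2).** A discontinued patient is one "randomized, but then withdrawn by investigator or subject withdraws consent". For completion, "Subjects are considered completed when they are followed through to day 29, had an adverse event or death occurred prior to day 29". The sentence after that adds "Patients will be asked to have day29 and day 120 study visits as well". The enrolled period ends when a patient is discontinued or completes.

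**Analysis (6.2.1).** All analyses use "a modified intention-to-treat approach, which excludes randomized subjects who do not initiate an infusion of the study plasma". The primary comparison is a two-sided Fisher exact test at 0.05. I take the time point to be Day 15: a stray 29 follows it in the text, but the same section lists Day 29 as secondary.

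**Treatment and sample size (5.3.4, 6.1).** Treatment is one unit of plasma, given once. The planned size is 50 patients, 1:1, with no allowance for dropout.

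**What is absent.** No section retains outcome follow-up after withdrawal, says how an unknown Day 15 outcome is handled, or says whether a leaver and the replacement are both analysed.

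**The concern.** After a single infusion no study treatment is left to stop. Withdrawal of an infused patient can therefore only mean the end of study procedures and data collection. If it happens before Day 15, the primary outcome may be lost, and a patient's course in hospital can plausibly influence both the wish to leave and the decision to withdraw.

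Replacement does not repair this. The new patient is a separate randomization with a separate prognosis and says nothing about the outcome of the one who left. It restores the head count, which makes the loss easy to overlook.

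Sections 5.3.3 and 6.2.1 also do not fit together. The analysis set keeps the infused leaver, but the plan secures no outcome for that patient, and 5.3.3 brings in another patient. An analyst would have to choose how to count the two after the data are in.

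**Working it through.** **1. The plan's own figure.** Section 6.1 tabulates a Fisher rejection region at 25 per arm. By two-sided Fisher test:

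| Control events | Active events (limit in 6.1) | p |
|---|---|---|
| 5 | 0 | 0.0502 |
| 6 | 1 | 0.0983 |
| 7 | 1 | 0.0488 |
| 8 | 1 | 0.0232 |
| 9 | 2 | 0.0374 |
| 10 | 3 | 0.0507 |

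The rows for 7, 8 and 9 control events reproduce. The other three do not reject at 0.05. That is a separate matter, and only the three rows that reproduce are used in steps 2 and 3.

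**2. One leaver in the active arm.** Take 7/25 control v 1/25 active among patients with known outcomes, where one active patient was infused, left and was replaced. The probability of x active events among m events in total is C(n1,x)·C(n0,m−x)/C(n1+n0,m). The two-sided p sums all tables no more probable than the one observed.

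- Leaver not counted, 1/25 v 7/25, m=8: x=1 has 25×480,700/536,878,650 = 0.0224, and x=0 has 1,081,575/536,878,650 = 0.0020. The other tail is the same, so p = 2×0.0244 = **0.049**.
- Leaver kept as an event, 2/26 v 7/25, m=9: x=2, 1, 0 have 0.0514, 0.0092, 0.0007; x=8, 9 have 0.0128, 0.0010. Sum **0.075**.
- Leaver kept as a non-event, 1/26 v 7/25, m=8: x=1, 0 have 0.0196, 0.0017; x=8 has 0.0025. Sum **0.024**.

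The three ways of counting fall on both sides of 0.05, and the plan does not choose among them.

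**3. Other tables, replaced active leavers kept as events.**

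| Leavers not counted | p | Leavers kept as events | p |
|---|---|---|---|
| 8/25 v 1/25 | 0.023 | one: 8/25 v 2/26 | 0.039 |
| 8/25 v 1/25 | 0.023 | two: 8/25 v 3/27 | 0.093 |
| 9/25 v 2/25 | 0.037 | one: 9/25 v 3/26 | 0.052 |

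Some results change side with one leaver and some do not.

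**4. Error rate under assumed selective loss.** Suppose plasma has no effect and the event rate is p. A share q of would-be events in the active arm leaves before being recorded, is not counted, and is replaced until 25 remain. The retained rate is p(1−q)/(1−pq), and the expected number replaced is 25pq/(1−pq). For p=0.32 (the assumption in 6.1) and q=0.2: 0.256/0.936 = 0.274 retained and 1.6/0.936 = 1.7 replaced. Summing binomial probabilities over the correct Fisher region gives the chance of falsely favouring convalescent plasma:

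| q, active arm only | Replaced at p=0.32 | False rejection, p=0.32 | False rejection, p=0.20 |
|---|---|---|---|
| 0 | 0 | 1.2% | 1.1% |
| 10% | 0.8 | 1.8% | 1.6% |
| 20% | 1.7 | 2.7% | 2.3% |
| 30% | 2.7 | 4.2% | 3.3% |
| 50% | 4.8 | 10.4% | 7.0% |

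With the same loss in both arms at p=0.32, the two-sided rate is 2.2–2.3%, against 2.4% with full follow-up. There is no inflation, but the event rates are understated.

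**The case against.** The strongest reply is that 6.2.1 already protects the comparison: only patients who never start an infusion are excluded, so an infused leaver is still analysed. Most exits would be of inpatients within about two weeks, and medical records are the primary source documents (9.6.1), so the outcome would often be available. Sensitivity to one patient is mainly a property of 25 per arm, and one-arm loss of 10–20% of events leaves false rejection near the nominal 2.5%.

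Much of this stands. It does not close the gap: availability of the record is not an instruction to use it after withdrawal, and the analysis-set rule supplies no outcome.

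A reader might infer more than the text supports:

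- *That investigator-withdrawn patients are replaced.* This is a possible reading, since 5.2 puts both kinds of exit under one label, but the replacement item speaks only of patients who withdraw.
- *That any adverse event removes a patient and triggers a replacement.* The adverse event definition in 7.2 is wide ("Any untoward medical occurrence in a clinical investigation subject who has received a study intervention"), and 5.2 sets no grade or relatedness limit. But a completed patient has not withdrawn. Later visits are still requested, the schedule in 5.4 has no adverse-event exception, and 7.3.1 follows reportable events to resolution.
- *That infused leavers are deleted from the analysis.* No section says so, and 6.2.1 implies the opposite.
- *That receiving a prohibited drug leads to withdrawal.* Section 5.3.8 attaches no such consequence, and 5.3.7 has COVID-19 treatments recorded.
- *That investigators would withdraw patients differently by arm.* Section 5.3.4 concedes only that nurses may know the arm, apart from the designated unblinded research assistant and the provider who orders the plasma. It aims to keep investigators, participants and the primary care team blinded, so differential exit cannot be excluded but is not shown.

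**Conclusion.** The point holds as a gap between two rules. Replacement is open to infused patients and the analysis set retains them, but nothing secures their Day 15 outcome or says how they and their replacements are counted. Followed as written, the plan can lose prognosis-related outcomes behind a restored head count.

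The size is real but illustrative. One infused leaver can move a boundary result across 0.05 (0.049 to 0.075), while 8/25 v 1/25 survives one such leaver. The error-rate figures assume that losses are selective, confined to the active arm and left out of the analysis, which is a worst case. The documents give no dropout rate, so neither the number of exits nor their balance between arms is known. The completion definition is a defective label that might be read as ending follow-up. It is not a route to replacement. This should be fixed before the analysis is locked, but it does not invalidate the design.

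**What to change.** In 5.3.3:

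- Limit replacement to randomized patients who withdraw before the infusion starts.
- State that withdrawal or non-compliance after infusion ends study procedures only. Ventilation/ECMO and vital status at Days 15 and 29 are still taken from the medical record unless the patient refuses this as well.
- State that every infused patient is analysed in the assigned arm, as 6.2.1 already implies.

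In 6.2.1, state in advance how a Day 15 outcome that remains unknown is counted, with a sensitivity analysis that counts it the other way.

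In 5.2, remove the adverse-event clause from the definition of a completed patient so that it cannot be read as ending follow-up.

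The cost is protocol wording. The data source is already in use. The downside is that a few infused leavers will have less complete secondary data and will not be replaced.
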